7.1 Medical Record Review

N/A

CONFIDENTIAL

7.2 Physical Examination

N/A

7.3 Vital Signs

N/A

7.4 Laboratory Evaluations

N/A

7.5 Pregnancy Testing

Although there are no known risks related to MRI on pregnant women or a fetus, there is a possibility of yet undiscovered pregnancy related risks. Since there is no possible benefit from participating in this protocol for a pregnant woman, we will exclude pregnant women. All women of child bearing potential are asked if they are using a reliable method of birth control and are required to attest that they are not pregnant before study visit and on the TMS safety screening form: 2018.12.07_TASS_832232

7.6 Efficacy Evaluations

- Single pulse TMS probes in the MRI scanner at 120% RMT, 77 pulses at 2.4 second each

7.7 Safety Evaluations

The primary investigator will routinely monitor and evaluate study procedures for potential increased risk.

8 Statistical Plan

Efficacy within subjects: Repeated measures ANOVA will be used to assess changes from baseline to post-stimulation for each task condition.

Efficacy between subjects: neuro-response rates and time to response will be compared with published rates within the literature to extrapolate the significance of this modality.

9 Safety and Adverse Events

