1.2 Name and Description of the Investigational Product

IDE Exempt

2 Study Objectives

- 3 This protocol aims to determine what neural systems underlie TMS-evoked brain responses and how the addition of a task organizes and augments this response to induce plasticity. We first determine which tasks known to activate DLPFC alone or in combination with TMS have greater activation of the DLPFC and have maximal anti-correlation with the subgenual cingulate. In addition, tasks will be combined with TMS in a sham controlled double-blind experiment to test neuromodulation-induced effects. In a sample of 25 healthy participants we will conduct a series of experiments to examine

CONFIDENTIAL

task effects, task-specific TMS augmentation effects and task-specific augmentation of TMS neuromodulation.

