Aim 3: to determine the effect of neuromodulation on DLPFC activation healthy participants will be randomized to one of the 3 task conditions: high-load cognitive SST, high-load IAPS task, or low-load SST (sham task condition). Following a 4 session course (2 session separated by at least 4 hours on one day, followed by 2 sessions separated by at least 4 hours on a second day) of either active rTMS or sham TMS neuromodulation in combination with the task condition participants will again have probe sessions in the scanner where DLPFC activation and connectivity will be determined. Following a 2-week interval, participants will receive the other stimulation condition (sham TMS if active first and active TMS if sham first).

[figure not shown]
Hypothesis 3a: Task (any of the 3) + active rTMS will result in greater DLPFC activation and greater dIPFC/sgACC anticorrelation than task plus sham rTMS

Hypothesis 3b: the IAPS task in combination with active rTMS will produce greater activation than the cognitive SST + active TMS or than control task + active TMS.

CONFIDENTIAL

4 Investigational Plan

Below is an example of the proposed study flow after screening visit. Please refer to attached task descriptions for further information:

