6.2 Study Intervention Phase

6.2.1 MRI Visits

- Verify & sign MRI Safety Screening Form
- Undergo MRI with tasks
 - Baseline MRI – tasks in the scanner, no TMS probe
 - Visit 1 – tasks in the scanner with TMS

6.2.2 Prior to Baseline MRI – Randomized order of learning all 3 study tasks (SST, IAPS, and Sham) in the scanner without TMS.

6.2.3 Visit 1 – in the scanner participant completes all 3 tasks, in previously randomized order with TMS.

6.2.4 After Visit 1 – Randomized to SST task only, IAPS task only, or Sham task only & either Active rTMS + task or Sham rTMS + task

5.2.5 Neuromodulation & MRI Probe Visits:

- Visits 2 & 3: Complete randomized task alone & again with randomized rTMS group
 - Confidence rating
- Visits 4 & 5: Complete randomized task alone & again with opposite rTMS group
 - Confidence rating
- MRI probes: in the scanner, participant completes randomized task alone & then with TMS probe.

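### Aim 3 (secondary): Section 8 specifies pre-post change for each task condition, not the active-versus-sham contrast that Hypothesis 3a states

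*Combined protocol and SAP*

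**What the plan says.** Section 8 (Statistical Plan) has two sentences, and the Statistical Methodology row of the Study Summary repeats them. Within subjects: "Repeated measures ANOVA will be used to assess changes from baseline to post-stimulation for each task condition". Between subjects: "neuro-response rates and time to response will be compared with published rates within the literature". Neither mentions sham, a stimulation factor, period or order, and no other section supplies an analysis for Aim 3.

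The objectives and design are more specific:

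- The Study Objectives say that "tasks will be combined with TMS in a sham controlled double-blind experiment to test neuromodulation-induced effects".
- Hypothesis 3a in Section 3.1 reads "Task (any of the 3) + active rTMS will result in greater DLPFC activation", and its comparator for activation and connectivity is given as "anticorrelation than task plus sham rTMS".
- Hypothesis 3b compares task groups under active stimulation: "the IAPS task in combination with active rTMS will produce greater activation than the cognitive SST + active TMS", and likewise against the control task.
- Aim 3 is a crossover: "Following a 2-week interval, participants will receive the other stimulation condition". Section 6.2.4 randomises each participant to one task and to "either Active rTMS + task or Sham rTMS + task" as the first course.

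Aim 3 is listed among the secondary objectives. The planned total is 25 participants.

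**The concern.** Aim 3 is the randomised, sham-controlled part of the study. Its hypothesis compares two stimulation conditions, pooled over tasks. Section 8 names a comparison over time, task by task, which is a different quantity.

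By the post-course scan a participant has repeated both the task and the scan. A baseline-to-post change therefore contains any practice, habituation or scanner drift as well as any stimulation effect. Upward drift would count towards stimulation and downward drift against it. The sham course is what separates the two, and it has no stated role in the analysis. If Section 8 is followed literally, a pre-post change could be reported where an active-minus-sham estimate is needed. Otherwise the analyst must choose the 3a contrast later, possibly with the data in view. Hypothesis 3b has no named contrast either, since the only between-subject comparison is with the literature.

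**Working it through.** **Inputs.** From the documents: 25 participants, three task groups (25/3 ≈ 8.3, so 8 or 9 each), two stimulation courses per participant, randomised first course. The documents give no alpha, power, SD, correlation, drift size or allocation ratio, so the sample size cannot be reproduced. Everything below assumes a two-sided 5% level, 80% power where relevant, and the stated ranges.

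**1. A pre-post test when stimulation does nothing.** Let the drift be d SD of the change score. A one-sample t test in n participants has noncentrality d√n. For n = 8 and d = 0.5 this is 0.5 × √8 = 1.414, against a critical value of 2.365 on 7 df.

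| Drift d | n = 8 | n = 9 |
|---|---|---|
| 0.1 | 5.7% | 5.8% |
| 0.3 | 11.4% | 12.5% |
| 0.5 | 23.2% | 26.3% |

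The size depends on how Section 8 is read. An active-only pre-post test over all 25 participants, with a change of 0.5 SD, is significant in about 67% of runs.

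**2. The direct contrast under the same drift.** The simulation used 20,000 runs per setting, 25 participants in groups of 8/8/9 and scan correlations of 0.2, 0.5 and 0.8. Drift was up to 0.5 SD in period 1 and up to 1.0 SD in period 2, with order splits of 13/12, 15/10 and 17/8. The period-adjusted active-minus-sham contrast rejected in 4.7% to 5.4%.

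**3. Cost of the period term for 3a.** In SD of the within-participant active-minus-sham difference:

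- Unadjusted paired test, 24 df: 2.920/√25 = 0.584.
- Model on the 25 differences with three task-group terms and one period term, 25 − 4 = 21 df: 2.938 × √((1/n₁ + 1/n₂)/4).

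| Order split | SE | Detectable effect | Increase over 0.584 |
|---|---|---|---|
| 13/12 | 0.2002 | 0.588 | 0.7% |
| 15/10 | 0.2041 | 0.600 | 2.7% |
| 17/8 | 0.2144 | 0.630 | 7.9% |

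Without the term, the paired contrast is biased by (n₁ − n₂)/25 of any period effect: 1/25 = 0.04 at 13/12 and 5/25 = 0.20 at 15/10. Under simple 1:1 randomisation (assumed), a split of 15/10 or worse has probability 42%, and 17/8 or worse 11%.

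**4. Precision for 3b as a difference between task groups in active minus sham.** If the two post-course scans correlate r, the SD of their difference is √(2(1 − r)) scan SD. The detectable effect is 2.938 × √(2(1 − r)) × √(1/n₁ + 1/n₂).

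| Assumed r | 8 versus 8 | 8 versus 9 |
|---|---|---|
| 0.2 | 1.86 | 1.81 |
| 0.5 | 1.47 | 1.43 |
| 0.8 | 0.93 | 0.90 |

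**5. Carry-over.** Suppose a fraction c of the active effect persists to the period-2 post scan. Active-first participants then show (1 − c) of the effect and sham-first participants show all of it. The period-adjusted estimate is the average, 1 − c/2: 0.95, 0.875 or 0.75 for c = 10%, 25% or 50% (assumed).

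**The case against.** The strongest reply is that repeated measures ANOVA is a suitable family of methods. Sham is called a stimulation condition in Aim 3, so the post-stimulation scans in Section 8 can include those after sham. Each participant has both courses, and Hypothesis 3a itself names the comparator. On this view an analyst would enter stimulation as a within-subject factor without being told. That stands as far as it goes. A reader might infer that the planned method cannot test 3a, and the documents do not support that. What remains is that Section 8 does name a contrast, and it is a different one.

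A reader might also infer that the missing period term leaves 3a untested. It does not. With randomised order, a paired active-minus-sham contrast without it still tests 3a, at some cost in bias if the orders are unequal. The term is a refinement.

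Nor are the 6% to 26% figures an error rate of the plan. They apply only if a per-arm pre-post result is offered as evidence for 3a, and only under the assumed drift. Nothing in the documents says that will happen.

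On 3b, one might simply compare the post-course scans of the task groups under active stimulation. That would not isolate neuromodulation. At the probe scans each group performs its own task (Section 6.2), so the difference would include ordinary task-evoked activation, which is the subject of Aim 1.

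**Conclusion.** The concern holds as a gap in specification that should be fixed, in a secondary aim. The contrast that Hypothesis 3a states and the crossover supports is not named, and the contrast that is named answers another question. A significant pre-post change would not be evidence for 3a. This conclusion rests on the wording and needs no numerical assumption.

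The sizes are illustrative. The gap between about 6% to 26% and about 5% depends on the assumed drift, on arms of 8 or 9, and on a pre-post result being used for 3a. The small cost of the direct contrast assumes 25 completers and a reasonably even order split. For 3b, precision is low on any assumption tried, from about 0.9 to 1.9 scan SD depending on the correlation between scans.

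**What to change.** In Section 8 and the summary:

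- **3a.** Name active minus sham over all participants as the estimate. Obtain it from a crossover ANOVA or linear mixed model on post-course DLPFC activation and, separately, on DLPFC/sgACC connectivity. Terms: stimulation, period, task group, stimulation-by-task group and a random participant effect.
- **3b.** Use the between-group difference in active minus sham. Alternatively, use the change under active stimulation from the pre-randomisation scan of the same task with TMS (Section 6.2.3). For the second option, first confirm that the low-load SST is scanned with TMS at that point: Section 6.2.3 says all three tasks are, whereas Section 4.1 lists stimulation alone, with SST and with IAPS. Report confidence intervals and say that precision is low and depends on the within-participant correlation.
- Keep per-task pre-post changes as descriptive, and state that the model does not remove carry-over.
- Reconcile the schedule so that the post-course scan of each period is identified. Section 5 puts scans after Visit 4, before Visit 6 and after Visit 8. The Section 6 table shows them at Visits 5 and 8, with none before Visit 6. Section 6.2 numbers the second course as Visits 4 and 5. The interval between periods also differs, being two weeks in Aim 3 and 7 to 14 days in Section 5.

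The cost is wording, the schedule reconciliation and three degrees of freedom (21 instead of 24). No scan is added to those already planned. The detectable effect for 3a rises by under 1% at 13/12 and by about 8% at 17/8, so stating how order is balanced would keep the cost at the low end.

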Recent use of psychoactive medications, as determined by investigators
Otherwise determined by investigator to be unfit for participation:
ex) meets DSM criteria for current alcohol or substance use disorder (in last 3 months)

**Investigational
Product (drug,
biologic, device, etc.)**

**For Device include
the planned use**

MagVenture X100 Stimulator - *please refer to the 'Devices in Research Form' attached to this submission*

**For Drug, food,
cosmetic, etc.**

MagVenture Cool B65 Coil - *please refer to the 'Devices in Research Form' attached to this submission*

include the dose,

route of

administration and

dose regimen

MagVenture MRI B91 Coil - *please refer to the 'Devices in Research Form' attached to this submission*

CONFIDENTIAL

This material is the property of the University of Pennsylvania.

Duration of administration (if applicable)	The neuromodulation participants will receive is FDA-approved iTBS at 120% RMT stimulation intensity; triplet 50 Hz bursts, repeated at 5 Hz; 2 s on and 8 s off; 600 pulses per session; for a total duration of 3 min 9 s per session to the 'Fitzgerald Target' (identified via MRI imaging). Sham TMS will also be administered at the aforementioned parameters.
Reference therapy	When in the scanner, participants will receive single pulse TMS probes while completing tasks at 120% RMT with 77 total pulses.
Statistical Methodology	Efficacy within subjects: Repeated measures ANOVA will be used to assess changes from baseline to post-stimulation for each task condition. Efficacy between subjects: neuro-response rates and time to response will be compared with published rates within the literature to extrapolate the significance of this modality.
Safety Evaluations	No data or safety monitoring board will be necessary for this protocol. The principal investigator will be responsible for monitoring this protocol.
Data and Safety Monitoring Plan	No data or safety monitoring board will be necessary for this protocol. The principal investigator will be responsible for monitoring this protocol.

CONFIDENTIAL

This material is the property of the University of Pennsylvania.

BACKGROUND AND STUDY RATIONALE

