Significance: this protocol builds on the RDoC construct of cognitive control to assess the neural substrates involved in TMS activation as well as task-induced TMS augmentation. By using both a passive vs active version of the SST working memory task we can examine the effect of manipulation characteristics of tasks and by using cognitive vs. emotional versions of the task we can probe the contribution of emotional arousal to the effects. Further by randomizing subjects to one of three task conditions (including a task control condition) we can determine the effect of task augmentation on TMS.

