3.1 Primary Objective

We will determine both an “intensity (difficulty) effect” and an “emotion effect” of task-induced fMRI activity in the scanner, collecting these measures in the same subjects. Participants will receive two working memory tasks:

1a) Sternberg Sorting Task (SST): a cognitive task comparing low-load vs. high-load conditions in which the picture stimuli are letters.

1b) International Affective Picture System (IAPS): an emotional task using IAPS picture that will also compare low load and high load conditions. The number of images will vary by condition load, but for both the high-load & low-load conditions, participants will look at IAPS pictures and answer questions about the images. Further, jittered within this design will be both neutral and negative blocks of IAPS pictures.

We will compare low-load vs. high-load brain activation and connectivity in the cognitive vs. emotional tasks.

Hypothesis 1a: Compared with the maintenance (low-load) SST condition, the high-load cognitive SST condition will produce greater DLPFC activation and dIPFC/sgACC anticorrelation.

Hypothesis 1b: Compared with the low-load IAPS emotional task, the high-load IAPS emotional pictures will produce higher activity in the DLPFC and dIPFC/sgACC anticorrelation.

Hypothesis 1c: The picture rating for arousal will be correlated with the activity in the DLPFC and dIPFC/sgACC anticorrelation.

Secondary Objectives:

Aim 2: to determine which task provides greater augmentation of the TMS-induced DLPFC activation, participants will receive in randomized order:

- 1) The cognitive SST working memory task or the IAPS task alone
- 2) rTMS + the cognitive SST working memory task or rTMS + the IAPS emotional task in randomized order. rTMS and the cognitive tasks will be conducted in the fMRI scanner where brain activation to a TMS probe and connectivity will be obtained.
- 3) rTMS alone

Hypothesis 2a: rTMS + either task will have greater DLPFC activation and greater dIPFC/sgACC anticorrelation than rTMS alone.

Hypothesis 2b: rTMS + the IAPS emotional working memory task will have greater DLPFC activation and greater dIPFC/sgACC anticorrelation than rTMS + cognitive SST (more robust)

Hypothesis 2c: rTMS + IAPS emotional task will have greater signal to noise (more selective).

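### Section 8 names no comparison of the randomised task groups for secondary Hypothesis 3b; its only between-subject analysis sets undefined response measures against published rates

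*Combined protocol and SAP*

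**What the plan says.** **Hypothesis.** Section 3.1, Aim 3, is listed under the secondary objectives. Each participant is randomised to one of three tasks: high-load SST, high-load IAPS, or low-load SST as the sham task. Each then has an active and a sham stimulation course in turn. Hypothesis 3b states that "the IAPS task in combination with active rTMS will produce greater activation than the cognitive SST + active TMS or than control task" with active stimulation. The outcomes come from "probe sessions in the scanner where DLPFC activation and connectivity will be determined".

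**Role of the randomisation.** The Significance paragraph in Section 1.1 says that "by randomizing subjects to one of three task conditions (including a task control condition) we can determine the effect of task augmentation on TMS".

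**Analysis.** Section 8 (Statistical Plan) has two sentences. The one labelled within subjects reads "Repeated measures ANOVA will be used to assess changes from baseline to post-stimulation for each task condition". The one labelled between subjects says that "neuro-response rates and time to response will be compared with published rates within the literature to extrapolate the significance of this modality". The Study Summary repeats both, the second beginning "Efficacy between subjects: neuro-response rates and time to response will be compared with published rates within the literature".

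**Probe scans.** Section 6.2 says of the MRI probes that "in the scanner, participant completes randomized task alone & then with TMS probe".

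**The concern.** The protocol randomises participants to tasks in order to learn whether the task changes the effect of stimulation, yet the statistical plan does not say how the task groups will be compared. The only analysis labelled between subjects looks outside the trial. In a comparison with published rates, differences in population, scanner, task and outcome definition cannot be separated from the intervention.

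At stake is one secondary hypothesis. If the text stays as it is, the analysis of 3b will be chosen after the data are seen, or the literature comparison will stand in for it.

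**Working it through.** The plan gives no figure to reproduce. The check sets the texts side by side, with one illustrative calculation of precision.

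**1. Is 3b between participants?** Yes. In Section 3.1 (Aim 3) and Section 4.1, each participant has one task. Only stimulation is crossed over. IAPS against SST, and IAPS against control, are therefore contrasts between randomised groups.

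**2. Does Section 8 name either contrast?**

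| Element needed for 3b | ANOVA sentence | Between-subjects sentence |
|---|---|---|
| Task group as a factor | not named | not named |
| Active/sham as a factor | not named | not named |
| Group contrast or interaction | not named | not named |
| Comparator | participant's own baseline | published rates |
| Outcome | change from baseline | neuro-response rate, time to response |

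Contrasts required by 3b: 2. Contrasts named: 0.

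**3. Are the between-subject measures defined?** No. Neuro-response and time to response appear only in Section 8 and its copy in the Study Summary. Aim 3 names DLPFC activation and connectivity. Section 7.6 (Efficacy Evaluations) lists single-pulse probes with no response threshold. No published comparator is identified.

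**4. Which outcome form suits the missing contrast?** Each group does its own task at the probe scan (Section 6.2). The protocol expects tasks to differ without any neuromodulation course: Hypothesis 1a for SST load, and Hypothesis 2b, under which "rTMS + the IAPS emotional working memory task will have greater DLPFC activation and greater dIPFC/sgACC anticorrelation than rTMS + cognitive SST". Write T for activation due to the scanner task, and N and S for the effects of the active and sham courses, assumed additive. For groups g and h:

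- Raw post-course activation, active only: (T_g + N_g) − (T_h + N_h) = (T_g − T_h) + (N_g − N_h). Scanner task and neuromodulation are mixed.
- Change from a same-task pre-course scan, active only: (T_g + N_g − T_g) − (T_h + N_h − T_h) = N_g − N_h. The task term cancels.
- Active minus sham: (T_g + N_g − T_g − S_g) − (T_h + N_h − T_h − S_h) = (N_g − S_g) − (N_h − S_h). The task term cancels here too.

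The second form keeps the literal hypothesis but needs a same-task baseline for every group. The third removes practice and sham responses but relies on no carryover between courses.

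**5. Do the documents settle those two conditions?** Not yet.

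- *Baseline.* Section 6.2 has every participant do all three tasks in the scanner, without TMS at the baseline MRI and with TMS at the next scan, before randomisation to a task. Section 4.1 lists the TMS conditions as rTMS alone, with SST and with IAPS, and does not name the low-load task there.
- *Schedule.* Section 5 places scans after Visit 4, before Visit 6 and after Visit 8. The table in Section 6 shows MRI at Visits 1, 2, 5 and 8. Section 6.2 numbers the visits differently again.
- *Interval.* Section 3.1 gives 2 weeks between courses; Section 5 gives 7 to 14 days.

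**6. What precision would a 3b contrast have?** N = 25 is from Section 5.5. Allocation of 8/8/9, two-sided 0.05, equal SDs and no carryover are assumptions. On participant differences, with 3 group terms and 1 period term, df = 25 − 3 − 1 = 21. The 95% half-width is t(0.975, df) × √(1/n1 + 1/n2):

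- 8 vs 8: 2.080 × √(1/8 + 1/8) = 1.04
- 8 vs 9: 2.080 × √(1/8 + 1/9) = 1.01
- If 20 complete (6/7/7, df = 20 − 3 − 1 = 16): 1.13 (7 vs 7) and 1.18 (6 vs 7)

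The unit is the SD of the participant-level difference. These widths describe a trial of 25, not the gap in Section 8.

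**The case against.** **The ANOVA may already be meant to include task group.** Section 8 refers to each task condition, and a mixed ANOVA with task as a factor is a natural extension. This partly stands: the ANOVA is under-specified rather than wrong, and extending it is the simplest remedy. But the sentence is labelled within subjects and names no group term. Separate tests of change in each group would not test a difference between groups.

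**The literature sentence may be context only.** If so, it does no harm, but then Section 8 has no stated between-group analysis.

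**A reader might infer that testing 3b under active stimulation would falsely credit scanner-task differences to neuromodulation.** That applies to raw post-course activation only. Section 8 speaks of change from baseline, and Section 6.2 describes pre-randomisation scans with all three tasks. With a same-task baseline, an additive task difference cancels. The documents therefore do not support a claim of inflated false positives in the stated analysis, and active-minus-sham is not the only acceptable contrast.

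**A reader might also infer that the scan schedule rules out a time to response.** That presumes response is timed across scans. The term is undefined, so only the lack of a definition is established.

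**This is a small mechanistic study.** True, and it limits the weight of the point. It does not explain why a stated hypothesis, with a randomisation serving it, has no named test.

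**Conclusion.** The point holds and should be fixed. Section 8 names 0 of the 2 group contrasts in Hypothesis 3b, and its only between-subject analysis uses undefined measures in a non-randomised comparison that cannot answer 3b. This rests on the text alone and needs no numerical assumption.

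It does not show that the stated ANOVA is biased, or that 3b's wording under active stimulation must be given up. The cancellation argument assumes additive task effects. The ±1 SD precision assumes near-equal groups and little dropout. The scope is one secondary hypothesis; this point does not assess whether Section 8 is adequate for Aims 1 and 2.

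**What to change.** In Section 8 and the Study Summary:

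1. Remove the comparison with published rates as an efficacy analysis, together with neuro-response rates and time to response. Keep a literature comparison at most as descriptive context.
2. Extend the repeated measures ANOVA, or use an equivalent mixed model, for DLPFC activation and for DLPFC/sgACC connectivity. Include task group as a between-participant factor, stimulation (active/sham), their interaction and period.
3. Test 3b with two contrasts, IAPS vs high-load SST and IAPS vs low-load SST, each with a 95% confidence interval.
4. Base them on change from a same-task pre-course scan under active stimulation, or on the active-minus-sham difference. Name in advance which is the main analysis and which is supportive. Do not use raw post-course activation under active stimulation alone.
5. State whether 3b requires both contrasts (no adjustment needed) or either one (adjust, for example by Holm). Its present wording leaves this open.

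First reconcile the visit numbering and scan schedule (Section 5, the table in Section 6, Section 6.2) and the interval between courses (Section 3.1 against Section 5). They determine which baseline exists and whether no carryover is plausible.

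**Cost.** Wording only, with no added participants; no added scans if the reconciled schedule keeps the scans already described. The 3b intervals will be wide, roughly ±1 SD with about 8 per group, and the write-up should say so.
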